1 BACKGROUND INFORMATION

1.1 Tenalisib (RP6530)

The phosphoinositide-3-kinases (PI3Ks) are a family of enzymes involved in various cellular functions, including cell proliferation and survival, cell differentiation, intracellular trafficking and immunity [1, 2, 3]. Tenalisib is a highly specific and orally available dual PI3K δ/γ inhibitor with nano-molar inhibitory potency and several fold selectivity over α and β PI3K isoforms. The specificity of Tenalisib towards PI3K δ and γ is evidenced by >1000 and >100-fold selectivity over α and β isoforms in an enzyme-based assay. Chemically, Tenalisib is an iso-flavone substituted adenine.

Summary of pre-clinical evaluation 1.2

Tenalisib has equimolar potency against both PI3K δ/γ isoforms in enzyme, cell, and bloodbased assays. Additionally, the compound inhibited antigen-induced superoxide or cytokine release from primary human neutrophils or monocytes at nano-molar concentration indicating a potential in modulation of the tumor microenvironment. Studies using immortalized B and T lymphoma cell lines demonstrated the anti-proliferative effect of Tenalisib coupled with induction of apoptosis and a concomitant inhibition of the downstream biomarker, pAKT. Similarly, cytokine induced pAKT was inhibited in malignant primary cutaneous T cell lymphoma (CTCL) cells isolated from patient donors.

Pre-clinical experiments demonstrated that Tenalisib is highly effective at killing primary CLL cells in vitro. The effect appeared to be equal to the Bruton tyrosine kinase (BTK) inhibitor- ibrutinib. In fact, the calculated IC₅₀ was slightly lower for Tenalisib than ibrutinib (362 nM, versus 567 nM). In comparison, the IC₅₀ for Tenalisib was lower than IC₅₀ for the conventional chemotherapy agents fludarabine (14.8 µM), bendamustine (382 µM), and chlorambucil (152 µM). Tenalisib also induced 50-60% reduction in chemokine induced migration of Daudi cells (in vitro surrogate for CLL patient B-cells), indicating the potential of the molecule in modulating tumor microenvironment [4].

In vivo efficacy of Tenalisib was confirmed in a subcutaneous mouse MOLT-4 xenograft model representative of human T-cell acute lymphoblastic leukemia. Oral administration of 50 mg/kg/BID over an 18-day period resulted in a significant delay in tumor growth [5].

In 28-days toxicity studies in rat and dog, once daily oral administration of Tenalisib was well tolerated. Target organ effects were observed in thyroid and liver. The no-observedadverse-effect level (NOAEL) was 20 mg/kg/day in rat and 10 mg/kg/day in dog. Refer to Investigator's Brochure (IB) for detailed background information on Tenalisib [4].

Summary of clinical evaluation

To date, Tenalisib has been evaluated in five clinical trials. Status of the studies as follows:

- 1. A Phase I Dose Escalation Study Evaluating the Safety and Efficacy of RP6530, a dual PI3K δ/γ inhibitor, in Patients with Relapsed or Refractory Hematologic Malignancies (European study: Protocol Number RP6530-1301). Status: Completed
- 2. A Phase I/Ib, Dose Escalation Study to Evaluate Safety and Efficacy of RP6530, a dual PI3K δ/γ inhibitor, in Patients with Relapsed or Refractory T-cell Lymphoma (US study: Protocol number RP6530-1401). Status: Completed
- 3. An open label, randomized, single dose, crossover study to evaluate food effects on relative bioavailability of RP6530 administered in fasting and fed conditions in healthy volunteers (Food effect study, Protocol no: RP6530-1501). Status: Completed

Protocol No: RP6530-1901 Version: 1.0, Dated 12 September 2019

- 4. An Open label, Phase II study to evaluate the efficacy and safety of Tenalisib (RP6530), a novel PI3K δ/γ dual inhibitor in adult patients with relapsed/refractory indolent Non-Hodgkin's Lymphoma (iNHL) (Protocol no.: RP6530-1802). Status: **Ongoing**
- 5. An Open label, Phase I/II study to evaluate the safety and efficacy of Tenalisib (RP6530), a novel PI3K δ/γ dual inhibitor given in combination with a histone deacetylase (HDAC) inhibitor, Romidepsin in adult patients with relapsed/refractory T-cell Lymphoma (Protocol no.: RP6530+Romidepsin-1805). Status: **Ongoing**

In addition, an open-label compassionate medication use study [Protocol:RP6530-1803; NCT03711604] is opened to allow ongoing patients with no evident disease progression to continue Tenalisib treatment.

• Safety of Tenalisib:

A total of 95 patients with relapsed/refractory hematologic malignancies were exposed to Tenalisib till date. In RP6530-1301 study, Tenalisib demonstrated acceptable safety profile up to 1200 mg BID and 800 mg TID without any dose limiting toxicity (DLT).

In RP6530-1401 study, a total of 58 patients were treated at Tenalisib 200 mg BID, 400 mg BID, 800 mg BID (Fasting) and 800 mg BID (Fed) in both dose escalation and expansion cohorts. Tenalisib demonstrated acceptable safety and tolerability profile up to 800 mg BID (Fasting). Reported DLTs included Grade 3 transaminitis, and Grade 3 skin rash. Tenalisib 800 mg BID (Fasting) was considered as maximum tolerated dose (MTD). Treatment related SAE were few and included pyrexia, raised international normalized ratio (INR), sepsis, skin infection, hypersensitivity, and diplopia secondary to neuropathy. Overall, Tenalisib has acceptable safety and tolerability profile up to 800 mg BID (Fasting).

• Pharmacokinetics (PK):

In RP6530-1301 study, maximum systemic exposures of Tenalisib were assessed on Cycle 1 Day 1 at doses 25 mg to 1200 mg BID; 600 and 800 mg TID. Based on C_{max} and AUC, dose proportionality was observed up to 400 mg dose. Dose related exposures were observed beyond 400 mg. There was no change in t_{max} on increasing doses however there was change in $t_{1/2}$. Steady state PK parameters of Tenalisib as determined on Cycle 2 Day 1 revealed no accumulation of Tenalisib. Similar PK profile was seen in RP6530-1401 study.

• Efficacy:

In RP6530-1301 study, Tenalisib demonstrated an ORR \approx 20% (CR: 7% and PR: 13%) in heavily pre-treated R/R patients with hematological malignancies. In RP6530-1401 study, response assessments of the thirty-five evaluable patients receiving at least two cycles of Tenalisib showed an ORR of 46% (CR: 9% and PR: 37%). Indication specific analysis showed an ORR of 47% (CR: 20%, PR: 27%) in PTCL and 45% (PR: 45%) in CTCL.

1.4 Study Rationale

1.4.1 Rationale for study population

Chronic Lymphocytic Leukemia (CLL) is a myeloproliferative neoplasm characterized by an accumulation of monoclonal mature B-cells (CD5+CD23+) in the blood, bone marrow, and secondary lymphatic organs. CLL is the most common form of adulthood leukemia.

The clinical course of CLL varies but it is typically a slowly progressing disease. The approximate 5-year survival rate for patients with CLL is 81.7% [6]. Due to infiltration of the bone marrow by lymphocytes, the principal complication of CLL is immunodeficiency

Version: 1.0, Dated 12 September 2019

related to myelosuppression and as a result, infection is the major cause of death in these patients [7].

Chromosomal abnormalities of 17p del, 11q del, and IGHV unmutated have been found to be markers of poor prognosis with a decrement in overall survival. Other markers of poor prognosis are β 2-microglobulin >3.5 mg/L, lymphocyte doubling time <12 months, and age > 60 years [8]. Treatment-related factors associated with poor prognosis include fludarabine refractoriness and relapse after 3 or more prior therapies [9].

Despite high response rates to initial treatment, relapse is common in CLL and relapsed/refractory disease is often characterized by resistance to chemotherapy. Among patients who either relapse or are refractory to first line treatment, the choice of subsequent therapy depends on age, duration of response to prior therapy, ability to tolerate treatment, disease related manifestations, and the presence of molecular poor-risk features. The majority of CLL patients receive intermittent treatment with periods of remission or stable disease. With each successive treatment regimen, many patients become refractory to treatment with diminished response rates and shorter response durations. Although newer agents Ibrutinib (BTK inhibitor), Venetoclax (BCL-2 inhibitor), Idelalisib (PI3K δ inhibitor), Duvelisib (PI3K δ / γ inhibitor) have become available for the treatment of CLL recently [10], CLL still remains an incurable disease for most patients and is still an unmet medical need.

Further, the safety and tolerability of newer agents remains a concern as there are high incidence of adverse events with use of these agents (e.g., atrial fibrillation, neutropenia, colitis and pneumonitis) leading to discontinuation of drug therapy. Therefore, there is ongoing need for safer and better treatment options.

Tenalisib is a highly specific and orally available dual PI3K δ/γ inhibitor with nano-molar inhibitory potency and several fold selectivity over α and β PI3K isoforms. Pre-clinical experiments demonstrated that Tenalisib is highly effective in killing primary CLL cells *in vitro*. The effect appeared to be equal to ibrutinib and higher than conventional chemotherapy agents. Tenalisib also demonstrated reduction in chemokine induced migration of Daudi cells, indicating its potential in modulating tumor microenvironment. Tenalisib has demonstrated clinical activity in patients with hematological malignancies with acceptable safety profile. Therefore, Tenalisib may offer a good treatment option for patient with relapsed/refractory CLL.

1.4.2 Rationale for dose selection

Maximum tolerated dose of Tenalisib (800 mg BID (Fasting)) was established in Phase I/Ib study and showed acceptable safety and promising efficacy in patients with peripheral and cutaneous T-cell lymphoma. Also, the same dose is being tested in a Phase II study in indolent NHL patients. Hence, 800 mg BID (Fasting) dose has been selected for CLL patient population.

1.5 Benefit and Risk

It is expected that the proposed single agent Tenalisib therapy has the potential to improve response rates in the relapsed/refractory CLL patient population. However, all the patients in clinical trials generally cannot expect to receive direct benefit from treatment during participation, as clinical trials are designed to provide information about the safety and effectiveness of an investigational medicine. In addition, there are certain risk associated with Tenalisib treatment which are described in section 3.5.5 of protocol. Additional details

Version: 1.0, Dated 12 September 2019

regarding specific benefits and risks for subjects participating in this clinical trial may be found in the accompanying IB and Informed consent documents.

2 TRIAL OBJECTIVES

2.1 Primary Objective

• To assess the anti-tumor activity of Tenalisib as determined by the objective response rate (ORR) and duration of response (DoR)

2.2 Secondary Objective

- To characterize safety and tolerability of Tenalisib.
- To assess progression free survival (PFS)

3 TRIAL DESIGN

3.1 Trial End Points

Efficacy:

- Overall response rate (ORR): ORR is defined as sum of CR and PR rates as defined by iwCLL guideline for CLL (Hallek *et al.* 2018).
- Duration of response (DOR): DOR is defined as the interval from the first documentation of CR/PR to first documentation of definitive disease progression or death from any cause.
- Progression-free survival (PFS): PFS is defined as the interval from first dose to first documentation of definitive disease progression or death from any cause.

Safety:

• Adverse Event (AE), Grade 3/4 AEs, Serious Adverse Event (SAE)

3.2 Design of Trial

The trial is a Phase II, open label, Simon's two stage study design to evaluate the efficacy and safety of Tenalisib in 61 patients with CLL who have relapsed or are refractory after at least one prior therapy. In Stage 1, 20 patients will be enrolled and the study treatment Tenalisib (800 mg BID) will be administered orally in 28-days of cycle over a period of 7 months (C1D1 to C8D1) in absence of definitive disease progression or unacceptable toxicity. If 8 or fewer responders are observed in this stage, the study will be terminated. Else, 41 additional patients will be enrolled into stage 2.

Patients will be evaluated for efficacy response by CT at C3D1±7 days, C5D1±7 days and C8D1±7 days and/or at End of the treatment (EOT) visit. The study will end when all ongoing subjects have reached their third tumor assessment on Cycle 8/Day 1 (C8D1) or have discontinued from the study for any reason, whichever is earlier. At the end of the study, all ongoing patients with no evident disease progression will be given the opportunity to enroll in an open-label compassionate medication use study [Protocol:RP6530-1803; NCT03711604] and will be followed up. The details of the study procedures are given in Study Assessments and Treatment Schedule (*Table 1*).

3.3 Data Review Committee (DRC)

The DRC will be constituted by the sponsor to review the safety and efficacy data. The committee will consist of PI of respective sites, sponsor representative, sponsor's medical expert, and a statistician. The DRC will meet and review the efficacy and safety data at regular intervals to assess the safety and efficacy of study drug and will provide recommendations.

Version: 1.0, Dated 12 September 2019

3.4 Randomization and Blinding

This is a non-randomized, open label study.

Investigational Medicinal Product

3.5.1 Dosage form and strengths

Two dose strengths of Tenalisib will be used in the study.

Investigational Product	Dosage form, strength	Manufacturer
Tenalisib	Tablets; 200 mg and 400 mg.	STA Pharma Co. Ltd

Note: Please refer Investigator's brochure for additional information of Tenalisib.

3.5.2 Labeling, packaging and supply

Tenalisib will be appropriately labeled and packaged as per local regulatory requirements and will be supplied by STA Pharma Co. Ltd through Rhizen Pharmaceuticals SA. Tenalisib will be available as 30 tablets per bottle. This must be kept in a secure place at below 25°C (77°F), protected from moisture".

3.5.3 Preparation and administration of the Investigational Product

At each visit, patients will be dispensed enough quantity of Tenalisib until the next visit. Study drug compliance should be reviewed at the beginning of each new treatment cycle. Study drug compliance will be documented, including missed doses and subject reeducation and dose administration.

Guideline for administration of Tenalisib:

- Method of Administration: Tenalisib will be administered orally twice daily.
- Pre-medications: None. No routine prophylactic anti-emetics or pre-medications should be given outside of protocol requirements. However, these medications may be administered for treatment of symptoms (see section 5.2).
- Tenalisib tablets will be self-administered orally twice daily one hour before a major meal (e.g. breakfast and dinner). Patients should not consume food during this one-hour period.
- Tenalisib tablets should be taken at approximately same time each day. Tablets should be swallowed; and should NOT be crushed or chewed.
- If a dose of Tenalisib is missed, it should be taken as soon as possible on same day with an interval of 8 hours between two doses. If it is missed for the entire day, it should not be repeated. If vomiting occurs, no attempt should be made to replace the vomited dose.
- Study drug compliance should be reviewed at the beginning of each cycle. Missed doses should be documented.

3.5.4 Accountability of Investigational Products

The site PI/ designee is responsible for accountability of all trial drug supplies (used/unused medication) at the site. The study monitor will verify receipt of investigational product at the sites during monitoring visit(s) and will conduct an inventory of remaining clinical trial supplies at the site close-out visit. All trial drug inventories must be made available for inspection by the monitor, sponsor representatives and regulatory agency inspectors/monitor upon request.

Version: 1.0, Dated 12 September 2019

Following monitor verification, returned or expired trial drugs can be destroyed according to local institutional policy with sponsor pre-approval of a site-specific destruction policy. Certificate of destructions will be filed at the site and in Trial Master File (TMF).

3.5.5 Precautions and risks associated with the Investigational Product

- Monitoring of liver enzymes and levels of TSH, T3, and T4 in subjects receiving Tenalisib is recommended based on target organ toxicity. Patients should be monitored for increased ALT/AST, skin rash, neutropenia as these events are reported with Tenalisib. Monitor patients for signs and symptoms of these events and interrupt Tenalisib for Grade 3 or higher event. In addition, monitor patients for diarrhea/ colitis and pneumonitis as these events are reported with agents of PI3K inhibitor class.
- Patients with CLL are at increased risk for infection (including sepsis and/or opportunistic infection with Pneumocystis *jirovecii* or Herpesviridae (herpes simplex virus, varicella-zoster virus, CMV, Epstein-Barr virus)) because of compromised immune function, which might be related to the disease itself and/or to the consequences of therapy. Therefore, monitor patients for signs and symptoms of infection and interrupt Tenalisib for Grade 3 or higher infection. The severity of infections should be quantified as minor (requiring either oral antimicrobial therapy or symptomatic care alone), major (requiring hospitalization and systemic antimicrobial therapy), or fatal (death as a result of the infection).
- Tenalisib shows moderate to high inhibition of CYP3A4 enzymes. Therefore, concomitant administration of Tenalisib with CYP3A4 substrates (e.g. calcium channel blockers, warfarin, carbamazepine, macrolide antibiotics, lovastatin, simvastatin, terfenadine) may reduce clearance of these drugs increasing the risk of adverse events. Similarly, as Tenalisib is inhibited by CYP3A4 and CYP2C9, there is possibility of drug interaction with inhibitors or inducers of CYP3A4 and CYP2C9. If concomitant treatment of these drugs is clinically warranted, careful observation of the patient is advised. Raised INR has been reported with concomitant warfarin administration. Therefore, use of heparin or warfarin to be avoided. Low molecular weight heparin (LMWH), Dabigatran or Edoxaban is advised for prophylaxis and treatment of venous thrombosis.
- Strong inhibitor or inducers should be avoided as directed in Section 5.3 on prohibited medication. Please refer to the recent Investigator Brochure for additional safety
- In absence of reproductive toxicity and genotoxicity data, the study participants should be advised to follow post treatment contraceptive measures.

The Expected Duration of Subject Participation and Follow-up

The expected duration of subject participation in the study is 7 months (C1D1 to C8D1). The study will end when all ongoing subjects have reached their third tumor assessment on Cycle 8/Day 1 (C8D1) or have discontinued from the study for any reason, whichever is earlier. At the end of the study, all ongoing patients with no evident disease progression will be given the opportunity to enroll in an open-label compassionate medication use study [Protocol:RP6530-1803] and will be followed up.

Study Stopping Rules

The following study stopping rules based on the safety and efficacy will be used.

Safety: The DRC will continue to monitor safety of Tenalisib (or toxicity trends that may be of concern) at interval of approximately 3 months from initiation of study until the completion of the study. In the event of one (1) death attributed to the study drug,

Version: 1.0, Dated 12 September 2019

study accrual will be suspended pending further investigation, and will only be resumed at the recommendation of the DRC. In addition, the DRC may recommend for termination of the study in case of major safety concerns.

• Efficacy: Once 20 patients are recruited in stage 1 of the study, the DRC will review the efficacy results and may recommend early termination of the study if there are 8 or fewer responders out of 20 patients. Else, 41 additional patients will be enrolled into stage 2.

In addition, Sponsor reserves the right to terminate the study in the interest of patient safety, for noncompliance with the protocol, lack of recruitment or any other administrative reasons. The sponsor and PIs will notify the regulatory authority and respective IRB/IEC respectively if the trial terminates early, with a justification for the early termination.

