7.4 Severity of Adverse events

Severity of adverse events will be assessed according to National Cancer Institute (NCI)- CTCAE v5.0 with exceptions for platelet, hemoglobin and ANC that are recommended by iwCLL guidelines for the CLL (see below).

Grade*	Decrease in platelet† or Hb‡ (nadir) from baseline, %	Absolute neutrophil count (nadir)§ x 10 ⁹ /L	
0	No change to 10	≥2	
1	11-24	\geq 1.5 and \leq 2	
2	25-49	$\geq 1 \text{ and } < 1.5$	

CONFIDENTIAL Page 40 of 61

Version: 1.0, Dated 12 September 2019

3	50-74	≥0.5 and <1	
4	≥ 75	< 0.5	

^{*} Grades: 1-mild; 2-moderate; 3-severe; 4-life-threatening; 5-fatal. Death occurring as a result of toxicity at any level of decrease from baseline will be recorded as grade 5.

§ If the absolute neutrophil count (ANC) reaches $<1\times10^9/L$, it should be judged to be grade 3 toxicity. Other decreases in the white blood cell count or in circulating granulocytes are not to be considered because a decrease in the white blood cell count is a desired therapeutic end point. A gradual decrease in granulocytes is not a reliable index in CLL for stepwise grading of toxicity. If the ANC is $<1\times10^9/L$ before therapy, the patient is not evaluable for toxicity referable to the ANC. The use of G-CSF is irrelevant for the grading of toxicity but should be documented.

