7.6.2 Overdose

Both intentional (misuse/abuse) and unintentional (accidental) overdose must be reported in the CRF. Symptomatic unintentional and intentional overdose must be reported as AE in the CRF (see below). Any accidental overdose with the study drug that is symptomatic, fulfilling a seriousness criterion, is to be reported to the Sponsor immediately (within 24 hrs) as SAE. Intentional overdose should be reported as an SAE irrespective of seriousness criteria.

CONFIDENTIAL Page 43 of 61

Version: 1.0, Dated 12 September 2019

Type of overdose	Document in AE in CRF CRF		Complete SAE form	
Unintentional (accidental)	Yes	Only if associated with an AE	Only if associated with an SAE	
Misuse/Abuse	Yes	Yes	Yes, even if not associated with a SAE	

7.7 **Dose Modifications**

In case of the hematologic and non-hematologic toxicities, the dose modifications provided below (Table 4 and Table 5) should be used a guidance and should be determined as per PI's clinical judgement. The dose modifications are intended to be applied when the investigator determines the events related to Tenalisib. If events (cytopenia) are deemed related to the underlying disease rather than Tenalisib, dose reduction will be done as per the investigator's discretion.

In case of drug withhold, Tenalisib treatment can be resumed if:

- Patient recovered from grade 3-4 toxicity as defined in dose modification guidance below.
- No clinical or radiographic evidence of disease progression.
- Investigator believes the risk of progression outweighs the risk of further treatment.

If treatment is delayed >2 weeks, treatment continuation should be discussed with Medical monitor. The treatment should be permanently discontinued if withhold of study drug due to drug related toxicity is for > 28-days unless approved by medical monitor.

At the discretion of the investigator, a dose re-escalation may be permitted for patients who earlier has dose reduction. The decision should be taken after evaluating the emerging safety data and benefit and risk of re-escalation. Drug holidays are discouraged. Any patient in whom similar toxicity recurs at the reduced dose, it should be discussed with medical monitor to determine appropriate strategy on treatment continuation.

Table 4: Dose Modifications for Hematologic Toxicity

CTCAE Grade Toxicity	Action to be Taken			
Hematologic				
Neutropenia (ANC)				

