Grade 3 $1.0 \times 10^9/L < ANC \ge 0.5 \times 10^9/L$	Maintain Tenalisib dose. Monitor ANC at least weekly.			
Grade 4 0.5 x 10 ⁹ /L <anc< td="">First incidence: Withhold* dose until resolved to ≤ Grade 2 or baseline. Monitor ANC at least weekly. Resume treatment at the same dose level. Subsequent occurrence: Hold dose until resolved to ≤ Grade 2 or baseline. Consider growth factor support. Resume treatment at the reduced dose level (Tenalisib 400 mg BID) if warranted.	</anc<>	First incidence: Withhold* dose until resolved to ≤ Grade 2 or baseline. Monitor ANC at least weekly. Resume treatment at the same dose level. Subsequent occurrence: Hold dose until resolved to ≤ Grade 2 or baseline. Consider growth factor support. Resume treatment at the reduced dose level (Tenalisib 400 mg BID) if warranted.			
Grade 3 Febrile neutropenia ANC <1.0 X 10 ⁹ /L with a single temperature of > 38.3 °C (101 °F)	Withhold* dose until resolved to ≤ Grade 2 or baseline, consider growth factor support, then reduce by 1 dose level (Tenalisib 400 mg BID), if warranted. If the			

CONFIDENTIAL Page 44 of 61

or a sustained temperature of \geq 38 °C (100.4 °F) for more than one hour.	ANC is <1 X 10^9 /L $(1000/\mu L)$ before therapy, the dose shall not be modified as long as ANC >0.5 X 10^9 /L.		
Thrombocytopenia			
Grade 3 thrombocytopenia [#] with Grade 1 bleeding	Maintain Tenalisib dose. Monitor platelet count at least weekly.		
Grade 3 thrombocytopenia [#] with Grade 2 bleeding	1st occurrence : Withhold** dose until to ≤ Grade 2 or baseline or resolution of bleeding. Consider platelet transfusion as necessary. Resume treatment at the same dose level.		
OR Grade 4 thrombocytopenia [#] (20.0 X 10 ⁹ /L< PLT)	Subsequent Occurrences: Withhold dose until to ≤ Grade 2 or baseline or resolution of bleeding. Consider platelet transfusion as necessary. Resume treatment at the reduced dose level (Tenalisib 400 mg BID) if warranted. Doses should not be modified if Grade 4 thrombocytopenia is present at baseline.		

^{*} The treatment should be permanently discontinued if withhold of study drug due to drug related toxicity is for > 28days unless approved by medical monitor.

** Patient receiving concomitant medication (e.g. anti-platelets, aspirin, or low molecular weight heparin) should be

Table 5: Dose Modifications for Non-Hematologic Toxicities

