Non- Hematologic	Action to be Taken Grade 3 or higher sepsis or pneumonia Withhold Tenalisib until infection has resolved. Restart at the same or at the reduced dose (Tenalisib 400 mg BID)			
Infection				
Skin rash	Grade 1-2			
(Cutaneous reactions)	 Maintain Tenalisib dose. Initiate supportive care with emollients, antihistamines (for pruritus), or topical steroids Monitor closely until resolved. 			
	Grade 3			
	 Withhold Tenalisib dose. Initiate supportive care with emollients, antihistamines (for pruritus), or topical steroids Monitor at least weekly until resolved. 			
	Restart Tenalisib at the reduced dose level (Tenalisib 400 mg BID).			
	If severe cutaneous reaction does not improve, worsens, or recurs, discontinue Tenalisib			
	Life threatening or SJS, TEN, DRESS (any grade)			
	Discontinue Tenalisib permanently.			
Pneumonitis	Moderate (Grade 2) symptomatic pneumonitis			
without suspected	• Withhold Tenalisib dose. Initiate systemic steroid therapy. If pneumonitis recovers to Grade 0 or 1, Tenalisib may be resumed at reduced dose.			
infectious cause	• If non-infectious pneumonitis recurs or patient does not respond to steroid therapy, discontinue Tenalisib.			

CONFIDENTIAL Page 45 of 61

discussed with the medical monitor for further management.

[#] Refer iwCLL criteria

	Severe (Grade 3) or life-threatening pneumonitis
	Discontinue Tenalisib. Treat with systemic steroid therapy.
NI C	Moderate diarrhea and responsive to antidiarrheal agents:
Non-infectious Diarrhea	Maintain Tenalisib dose. Monitor at least weekly until resolved.
	Moderate diarrhea and unresponsive to antidiarrheal agents:
	• Withhold Tenalisib dose. Initiate supportive therapy with enteric acting steroids (e.g., budesonide).
	Monitor at least weekly until resolved.
	• Restart Tenalisib at the reduced dose level (Tenalisib 400 mg BID).
	Severe diarrhea or hospitalization
	• Withhold Tenalisib dose. Initiate supportive therapy with enteric acting steroids (e.g.,
	budesonide) or systemic steroids.
	Monitor at least weekly until resolved.
	• Restart Tenalisib at the reduced dose level (Tenalisib 400 mg BID).
	Life threatening diarrhoea • Discontinue Tenalisib permanently.
Hepatic*	Transaminitis
Перапе	Grade 1-2 Transaminitis (ALT/AST >1-3 x ULN if baseline is normal; 1.5 - 3 x baseline
	if baseline is abnormal):
	Maintain Tenalisib dose and initiate prednisone 40 mg daily.
	Monitor AST/ALT weekly until resolved and then taper steroid.

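### Protocol 3.5.5 and Table 4 give opposite dosing instructions for drug-related, non-febrile Grade 3 neutropenia; Table 5 prints no transaminitis band for ALT/AST >3 to 5 x ULN with a normal baseline and leaves the Grade 2 withhold ambiguous

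*Protocol*

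**What the plan says.** **Neutropenia.** Protocol 3.5.5 lists increased ALT/AST, skin rash and neutropenia as events reported with Tenalisib and continues: "Monitor patients for signs and symptoms of these events and interrupt Tenalisib for Grade 3 or higher event". It makes no exception for neutropenia and does not point to section 7.7. Table 4 in section 7.7 gives this action for Grade 3 neutropenia without fever: "Maintain Tenalisib dose. Monitor ANC at least weekly". Grade 3 febrile neutropenia and Grade 4 neutropenia have their own rows, and both say to withhold.

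**Status of the tables.** Section 7.7 says that "the dose modifications provided below (Table 4 and Table 5) should be used a guidance", subject to the investigator's clinical judgement. It also limits their scope: "The dose modifications are intended to be applied when the investigator determines the events related to Tenalisib". Cytopenia put down to the underlying disease is left to the investigator.

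**ANC grading.** Section 7.4 sets Grade 3 at ANC at least 0.5 and below 1 x 10^9/L; once ANC falls below 1, "it should be judged to be grade 3 toxicity". If ANC was already below 1 before therapy, "the patient is not evaluable for toxicity referable to the ANC".

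**Transaminitis.** The first hepatic row of Table 5 is headed "Grade 1-2 Transaminitis (ALT/AST >1-3 x ULN if baseline is normal; 1.5 - 3 x baseline" (the baseline limb applies when baseline is abnormal). Grade 3 starts above 5 x and Grade 4 above 20 x. The first action in the Grade 1-2 row is "Maintain Tenalisib dose and initiate prednisone 40 mg daily", followed by weekly monitoring and a steroid taper. The last action is to withhold if Grade 2 develops or Grade 1 worsens, with a closing qualifier about being on steroids.

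**The concern.** An investigator who sees a related, non-febrile ANC of, say, 0.8 x 10^9/L finds an instruction to interrupt in one section and an instruction to continue in another. Sites could treat the same value differently and each be following the protocol.

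The hepatic row matters because the range missing from the printed limits lies directly below Grade 3 transaminitis, which Protocol 1.3 reports as a dose-limiting toxicity of this drug. At that level an investigator should not have to work out whether the protocol intends continued dosing with prednisone or a withheld dose.

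**Working it through.** No sample size, power or error rate is involved. The check sets the instructions side by side.

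**1. Where 3.5.5 and section 7.7 agree and disagree, for events judged related to Tenalisib**

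| Event | 3.5.5 | Tables 4 and 5 | Consistent? |
|---|---|---|---|
| Grade 3 neutropenia, no fever | interrupt | maintain, ANC at least weekly | no |
| Grade 3 febrile neutropenia | interrupt | withhold | yes |
| Grade 4 neutropenia | interrupt | withhold | yes |
| Grade 3 skin rash | interrupt | withhold | yes |
| Grade 3 transaminitis | interrupt | withhold | yes |

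One cell conflicts. Its limits come from three places:
- Section 7.4 gives the ANC range, at least 0.5 and below 1 x 10^9/L.
- The separate febrile row in Table 4 removes patients with fever.
- The ANC footnote in section 7.4 removes patients with ANC below 1 before therapy. Inclusion criterion 7a can admit such patients when the low count is due to marrow involvement.

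The restriction to related events is needed because section 7.7 applies its tables only to those. For a disease-related cytopenia, section 7.7 gives discretion rather than an instruction to maintain, so there is no exact contradiction.

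**2. Coverage of the printed ALT/AST bands, normal baseline, in multiples of ULN**

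- Grade 1-2: above 1, up to 3.
- Grade 3: above 5, up to 20.
- Grade 4: above 20.

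The bands leave out values above 3 and up to 5. The bilirubin entries in the same table run without a break (>1.5-3, >3-10, >10), so a gap is not the table's usual layout. The rows for other non-hematologic toxicity do not fill it, because transaminitis has its own entry.

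**3. Action for a patient first seen at Grade 2 and not yet on steroids**

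- If the steroid qualifier governs both halves of the withhold instruction, this patient continues Tenalisib and starts prednisone. Withholding follows only if Grade 2 develops on steroids.
- If the qualifier governs only worsening of Grade 1, this patient is withheld at once.

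The sentence allows both readings, and nothing else in the row decides between them.

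**The case against.** The strongest reply on neutropenia is that 3.5.5 is a general precaution covering three events in one sentence, whereas section 7.7 is the dedicated dosing section with a row for this exact grade. Most sites would follow the specific text, and the medical monitor can advise. That makes the conflict mild. It does not remove it: no precedence is stated, and calling the tables guidance under investigator judgement does not say that 3.5.5 yields to them.

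On transaminitis, the row is labelled Grade 1-2 and Grade 3 begins above 5 x, so >3 to 5 x can only be Grade 2. That stands. No patient is left without a row, and the printed limit is best treated as a misprint. A reader might also infer that the row flatly contradicts itself on Grade 2. The text does not support that, because it can be read as a sequence: treat and monitor first, withhold later. What remains is an ambiguity about the patient who presents at Grade 2.

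Two further inferences are tempting and should not be drawn.
- A reader might carry the gap over to the baseline scale and conclude that patients who enter with raised ALT/AST could reach very high multiples of ULN without meeting a printed band. The Grade 3 and Grade 4 rows do not restrict their ULN limits to a normal baseline, so such values can already qualify there. The point is therefore confined to a normal baseline.
- A reader might infer that the SAP 10.6.2 tally of adverse events leading to dose interruption or reduction is distorted. That tally is descriptive and correctly counts the interruptions that occurred, whichever text prompted them. Nothing shows that any patient had an affected event, and the plan does not provide for recording which text a site followed.

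**Conclusion.** The point holds as a minor correction to dosing-safety text. The neutropenia part is a real contradiction between two stated rules, limited to the one conflicting cell identified above. The transaminitis part is a misprinted upper limit plus an ambiguous withhold condition.

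The conclusion assumes that the event is judged related to Tenalisib, that the patient's ANC was at least 1 x 10^9/L before therapy, and that the ALT/AST baseline is normal. No frequency is claimed, because the documents give no event rates. The efficacy analyses and the two-stage design are untouched. SAP 5.1 records that the study has closed and that Stage 2 will not be performed, so the correction matters for the protocol text as it stands and for any later protocol that reuses it.

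**What to change.** - **Protocol 3.5.5:** replace the single instruction with wording such as *interrupt for Grade 3 or higher ALT/AST increase or rash; for neutropenia follow Table 4*. If the sponsor's medical expert intends interruption for non-febrile Grade 3 neutropenia, change the Table 4 row instead.
- **Table 5, Grade 1-2 transaminitis limits:** extend the upper limit to 5 x ULN, and to 5 x baseline if baseline is abnormal, so that the row meets the start of Grade 3.
- **Table 5, Grade 2 action:** state one action for Grade 2, including whether it depends on the patient already being on steroids.

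The cost is one sentence and one table row, plus a decision by the sponsor's medical expert on the intended action. It adds no procedures, patients or analyses.
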